## **APPENDIX 3: Pharmacokinetic and Immunogenicity Sampling Schedule for Obinutuzumab, Polatuzumab Vedotin, and Lenalidomide in Relapsed or Refractory Follicular Lymphoma Patients**

Appendix 3 has been clarified to include patients with R/R FL, removing information about patients with DLBCL.

## **APPENDIX 4: *Pharmacokinetic and Immunogenicity Sampling Schedule for Rituximab, Polatuzumab Vedotin, and Lenalidomide in Relapsed or Refractory DLBCL Patients***

Appendix 4 has been added. Subsequent appendices have been renumbered accordingly.

## **APPENDIX 5: *Modified Lugano Response Criteria for Malignant Lymphoma (Cheson et al. 2014)***

Appendix 5 has been revised to add “modified” to the title and to clarify designation of PET-CT based PR.

## **APPENDIX 12: *Diagnostic Criteria for Tumor Lysis Syndrome***

Appendix 12 has been added.

## **SAMPLE INFORMED CONSENT FORM**

The sample Informed Consent Form has been revised to reflect the changes to the protocol.

## PROTOCOL SYNOPSIS

**TITLE:** A PHASE Ib/II STUDY EVALUATING THE SAFETY AND EFFICACY OF OBINUTUZUMAB IN COMBINATION WITH POLATUZUMAB VEDOTIN AND LENALIDOMIDE IN PATIENTS WITH RELAPSED OR REFRACTORY FOLLICULAR *LYMPHOMA AND RITUXIMAB IN COMBINATION WITH POLATUZUMAB VEDOTIN AND LENALIDOMIDE IN PATIENTS WITH RELAPSED OR REFRACTORY DIFFUSE LARGE B-CELL LYMPHOMA*

**PROTOCOL NUMBER:** GO29834

**VERSION NUMBER:** 2

**EUDRACT NUMBER:** 2015-001999-22

**IND NUMBER:** 109409

**TEST PRODUCT:** Obinutuzumab (RO5072759)  
*Rituximab (RO0452294)*  
Polatuzumab vedotin (DCDS4501A; RO5541077)  
Lenalidomide

**PHASE:** Phase Ib/II

**INDICATION:** Follicular or diffuse large B-cell lymphoma

**SPONSOR:** F. Hoffmann-La Roche Ltd

### **Objectives and Outcome Measures**

This study will evaluate the safety, efficacy, and pharmacokinetics of induction treatment consisting of obinutuzumab in combination with polatuzumab vedotin and lenalidomide (G+Pola+Len) in patients with relapsed or refractory (R/R) follicular lymphoma (FL) *and rituximab in combination with polatuzumab vedotin and lenalidomide (R+Pola+Len) in patients with R/R DLBCL*, followed by post-induction treatment with obinutuzumab in combination with lenalidomide (G+Len) (*referred to as maintenance*) in patients with FL who achieve a complete response (CR), partial response (PR), or stable disease at end of induction (EOI) and *post-induction treatment with rituximab plus lenalidomide (R+Len) (referred to as consolidation)* in patients with DLBCL who achieve a CR or PR at EOI. Specific objectives and corresponding endpoints for the study are outlined below.

In this study, "study treatment" refers to the protocol-mandated treatments under study (i.e., obinutuzumab, *rituximab*, polatuzumab vedotin, and lenalidomide).

### **Safety Objective**

The safety objectives for this study are as follows:

- To determine the recommended Phase II dose (RP2D) for polatuzumab vedotin and lenalidomide when given in combination with a fixed dose of obinutuzumab *and the RP2D of lenalidomide when given in combination with a fixed dose of polatuzumab vedotin and rituximab* on the basis of the following endpoint:

Incidence of dose-limiting toxicities (DLTs) during the first cycle of study treatment

- To evaluate the safety and tolerability of G+Pola+Len and R +Pola +Len on the basis of the following endpoints *in the respective combinations*:
  - Nature, frequency, severity, and timing of adverse events, including DLTs
  - Changes in vital signs, ECGs, and clinical laboratory results during and following study treatment administration

### **Efficacy Objective**

Response will be determined on the basis of positron emission tomography (PET) and computed tomography (CT) scans or CT scans alone, using Revised Lugano Response Criteria for Malignant Lymphoma, hereinafter referred to as the Lugano 2014 criteria. Response will be determined by an Independent Review Committee (IRC) and by the investigator.

#### Primary Efficacy Objective

The primary efficacy objective for this study is to evaluate the efficacy of induction treatment with G+Pola+Len *in R/R FL* and R +Pola +Len *in R/R DLBCL* on the basis of the following endpoint:

- CR at EOI, as determined by the IRC on the basis of PET-CT scans

#### Secondary Efficacy Objectives

The secondary efficacy objective for this study is to evaluate the efficacy of induction treatment with G+Pola+Len and maintenance treatment with G +Len *in R/R FL* and of induction treatment with R +Pola +Len and consolidation treatment with R +Len *in R/R DLBCL* on the basis of the following endpoints:

- CR at EOI, as determined by the investigator on the basis of PET-CT scans
- CR at EOI, as determined *by the IRC and* by the investigator on the basis of CT scans alone
- Objective response (defined as a CR or PR) at EOI, as determined by the IRC and by the investigator on the basis of PET-CT scans
- Objective response (defined as a CR or PR) at EOI, as determined by the IRC and by the investigator on the basis of CT scans alone
- Best response of CR or PR during the study, as determined by the investigator on the basis of CT scans alone

#### Exploratory Efficacy Objective

The exploratory efficacy objective for this study is to evaluate the long-term efficacy of G+Pola+Len and R +Pola +Len on the basis of the following endpoints:

- For patients who have positive PET scans at EOI: CR at 12 months, as determined by the IRC and by the investigator on the basis of PET-CT scans *in FL patients*; CR at end of consolidation (EOC), as determined by the IRC and by the investigator on the basis of PET-CT scans, *in DLBCL patients*
- PFS, defined as the time from initiation of study treatment to first occurrence of disease progression or relapse, as determined by investigator on the basis of CT scans alone, or death from any cause
- EFS, defined as the time from initiation of study treatment to any treatment failure, including disease progression or relapse, as determined by investigator on the basis of CT scans alone, initiation of new anti-lymphoma therapy, or death from any cause, whichever occurs first
- Disease-free survival, defined, among patients achieving a CR, as the time from the first occurrence of a documented CR to relapse, as determined by the investigator on the basis of CT scans alone, or death from any cause, whichever occurs first
- Overall survival, defined as the time from initiation of study treatment to death from any cause

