## 2.2 EFFICACY OBJECTIVES

Response will be determined on the basis of positron emission tomography (PET) and computed tomography (CT) scans or CT scans alone, using Revised Lugano Response Criteria for Malignant Lymphoma (Cheson et al. 2014), hereinafter referred to as the Lugano 2014 criteria. Response will be determined by an Independent Review Committee (IRC) and by the investigator.

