### 2.2.3 Exploratory Efficacy Objective

The exploratory efficacy objective for this study is to evaluate the long-term efficacy of G+Pola+Len *and R +Pola +Len* on the basis of the following endpoints:

- For patients who have positive PET scans at EOI:
  - CR at 12 months, as determined by the IRC and by the investigator on the basis of PET-CT scans *in FL patients*
  - CR at end of consolidation (EOC), as determined by the IRC and by the investigator on the basis of PET-CT scans, *in DLBCL patients*
- PFS, defined as the time from initiation of study treatment to first occurrence of disease progression or relapse, as determined by investigator, or death from any cause

- EFS, defined as the time from initiation of study treatment to any treatment failure, including disease progression or relapse, as determined by investigator, initiation of new anti-lymphoma therapy, or death from any cause, whichever occurs first
- Disease-free survival (DFS), defined, among patients achieving a CR, as the time from the first occurrence of a documented CR to relapse, as determined by the investigator, or death from any cause, whichever occurs first
- Overall survival (OS), defined as the time from initiation of study treatment to death from any cause

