##### **4.5.5.1 Radiographic Assessments**

PET scans should include the base of the skull to mid-thigh region. Full body PET scans should be performed when clinically appropriate.

CT scans with oral and IV contrast should include chest, abdomen, and pelvic scans. CT scans of the neck should be included if clinically indicated (i.e., if evidence of disease upon physical examination) and must be repeated throughout the study if there is disease involvement at baseline.

PET-CT scans and diagnostic CT scans should be acquired according to a standardized imaging manual, which will be provided to all sites.

If contrast is medically contraindicated (e.g., patients with contrast allergy or impaired renal clearance), MRI scans of the chest, abdomen, and pelvis (and neck, if clinically indicated) and a non-contrast CT scan of the chest may be performed. If MRI scans cannot be obtained, CT scans without contrast are permitted as long as this allows consistent and precise measurement of the targeted lesions during the study treatment period.

The same radiographic assessment modality must be used for all response evaluations to ensure consistency across different timepoints (including unscheduled assessments).

A full tumor assessment, including radiographic assessment, must be performed any time disease progression or relapse is suspected.

Additional details regarding imaging procedures will be provided in the Imaging Manual.

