#### **5.3.5.10 Lack of Efficacy or Worsening of Lymphoma**

Events that are clearly consistent with the expected pattern of progression of the underlying disease should **not** be recorded as adverse events. These data will be captured as efficacy assessment data only. In most cases, the expected pattern of progression will be based on the Lugano 2014 criteria (see [Appendix 5](#)). In rare cases, the determination of clinical progression will be based on symptomatic deterioration. However, every effort should be made to document progression through use of objective criteria. If there is any uncertainty as to whether an event is due to disease progression, it should be reported as an adverse event.

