### **6.6.3 Exploratory Efficacy Endpoints**

Exploratory efficacy analyses will include estimation of the proportion of patients achieving each of the following endpoints:

- For patients who have positive PET scans at EOI:
  - CR at 12 months, as determined by the IRC and by the investigator on the basis of PET-CT scans, *in FL patients*
  - *CR at EOC, as determined by the IRC and by the investigator on the basis of PET-CT scans, in DLBCL patients*

Point estimates will be presented, along with the corresponding two-sided 90% Clopper-Pearson exact CIs. Patients without a post-baseline tumor assessment will be considered non-responders.

Exploratory efficacy analyses will also be performed on the following endpoints:

- PFS
- EFS
- DFS
- OS

PFS, EFS, DFS, and OS will be summarized descriptively using the Kaplan-Meier method ([Kaplan and Meier 1958](#)). For the PFS, EFS, and DFS analyses, data for patients without an event of interest will be censored at the date of the last tumor assessment. For patients without post-baseline tumor assessments, data will be censored at the date of initiation of study treatment plus 1. For the OS analysis, data for patients who have not died will be censored at the date the patient was last known to be alive. Where medians are reached, the corresponding estimated median will be provided, along with the 95% CI estimated using the method of [Brookmeyer and Crowley \(1982\)](#). In addition, landmark estimates of the proportion of patients who are

event free at 6 months, 9 months, 1 year, and 2 years will be provided, along with 95% asymptotic CIs using Greenwood's formula for standard errors.

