**Appendix 5**  
***Modified* Lugano Response Criteria for Malignant Lymphoma**  
**(Cheson et al. 2014) (cont.)**

Revised Criteria for Response Assessment		
Response and Site	PET-CT–Based Response	CT-Based Response
Progressive disease	Progressive metabolic disease	Progressive disease requires at least 1 of the following:
Individual target nodes/nodal masses	Score 4 or 5 b with an increase in intensity of uptake from baseline and/or	PPD progression
Extranodal lesions	New FDG-avid foci consistent with lymphoma at interim or end-of-treatment assessment	
An individual node/lesion must be abnormal with:
 
LDi > 1.5 cm and
 
Increase by ≥ 50% from PPD nadir and
 
An increase in LDi or SDi from nadir
 
0.5 cm for lesions ≤ 2 cm
 
1.0 cm for lesions > 2 cm
 
In the setting of splenomegaly, the splenic length must increase by > 50% of the extent of its prior increase beyond baseline (e.g., a 15-cm spleen must increase to > 16 cm). If no prior splenomegaly, must increase by at least 2 cm from baseline.
 
New or recurrent splenomegaly
 
New or clear progression of preexisting non-measured lesions

## Appendix 5

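### Progression for PFS, EFS and DFS is defined on CT alone in the Synopsis and with no stated modality in Section 2.2.3; under the CT-only text, failures called on PET-CT or symptoms are censored because they failed

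*Combined protocol and SAP*

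**What the plan says.** The Synopsis (Exploratory Efficacy Objective) defines the PFS event as the "first occurrence of disease progression or relapse, as determined by investigator on the basis of CT scans alone, or death from any cause". Its EFS and DFS definitions carry the same CT restriction. Section 2.2.3 defines PFS by the "first occurrence of disease progression or relapse, as determined by investigator, or death from any cause", and its EFS and DFS definitions also omit the CT words. Both texts are current; neither comes from the summary of changes.

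The general statement in Section 2.2 leaves both routes open: "Response will be determined on the basis of positron emission tomography (PET) and computed tomography (CT) scans or CT scans alone". Section 6.6 repeats that choice, and Section 6.6.3 only lists the endpoints by name.

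Two other places allow progression to be called without a CT finding. Appendix 5 has a PET-CT category of progressive metabolic disease, separate from the CT criteria, which includes "New FDG-avid foci consistent with lymphoma at interim or end-of-treatment assessment". Section 5.3.5.10 says: "In rare cases, the determination of clinical progression will be based on symptomatic deterioration".

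Section 6.6.3 gives the censoring rules. For PFS, EFS and DFS, "data for patients without an event of interest will be censored at the date of the last tumor assessment". It then adds: "For patients without post-baseline tumor assessments, data will be censored at the date of initiation of study treatment plus 1".

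**The concern.** The same patient can have an event under one text and be censored under the other. Two analysts working from this protocol could therefore report different curves from the same data.

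The CT-only text also interacts badly with follow-up. Section 4.6.2 stops study treatment at disease progression. Section 3.1.6 then follows progressed patients only for survival status and new anti-lymphoma treatment. A patient declared progressive without CT progression may never have a later CT that could supply the event, so the curve treats that patient as still at risk up to the last scan and then as uninformatively lost. The loss is in fact caused by failure. The design is open-label and non-randomized, so there is no concurrent arm in which the same bias would appear and cancel.

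**Working it through.** No sample size, alpha or event count is stated for these endpoints, so the main check is a comparison of texts, followed by a small illustration.

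**1. Patients traced under the CT-only text**

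| Patient | PFS | EFS | DFS |
|---|---|---|---|
| CT shows progression | Event | Event | Event (relapse after CR) |
| Called progressive on PET-CT or symptoms; scanned after baseline; no CT progression; no death recorded | Censored at last tumor assessment | Same, unless new therapy is recorded (event) | Censored at last tumor assessment |
| Called progressive on symptoms; no scan after baseline; no death recorded | Censored at treatment start plus 1 | Same, unless new therapy is recorded (event) | Not possible: DFS starts at a documented CR, so a post-baseline assessment exists |
| Either of the two rows above, death recorded later | Event at death, later than the failure | Event at the earlier of new therapy and death | Event at death, for patients with a documented CR |

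Under Section 2.2.3 with a broader reading of the modality, the second and third rows become events when the investigator makes the call.

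**2. The plus-1 date.** The plan gives no unit. Read as one day, Day 1 + 1 = Day 2. The row is reachable because the first on-treatment CT is due within 7 days before Day 1 of Cycle 3, and end-of-induction imaging is done only after at least two induction cycles (Appendices 1 and 2).

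**3. Timing of a PET-only call at end of induction.** With six undelayed cycles, Day 1 of Cycle 6 falls 5 × 28 = 140 days after treatment start. The assessment follows 6 to 8 weeks later, at 140 + 42 = 182 to 140 + 56 = 196 days. Censoring there would mainly affect the 9-month, 1-year and 2-year landmarks in Section 6.6.3.

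**4. Illustration for the plus-1 case at 6 months.** Inputs: n = 40 (expansion cohort per histology, Section 6.1). Assumed: k patients with clinical progression, no post-baseline scan and no recorded death; a share S of the other patients event-free at 6 months; no other censoring. With e = (n − k)(1 − S), rounded to whole patients:

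- k counted as events: (n − k − e)/n
- k censored at plus 1: (n − k − e)/(n − k)
- difference before rounding: S × k/n

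| k | S | e | As events | Censored at plus 1 | Difference |
|---|---|---|---|---|---|
| 2 | 0.5 | 19 | 19/40 = 47.5% | 19/38 = 50.0% | 2.5 points |
| 2 | 0.6 | 15 | 23/40 = 57.5% | 23/38 = 60.5% | 3.0 points |
| 2 | 0.7 | 11 | 27/40 = 67.5% | 27/38 = 71.1% | 3.6 points |
| 4 | 0.5 | 18 | 18/40 = 45.0% | 18/36 = 50.0% | 5.0 points |
| 4 | 0.7 | 11 | 25/40 = 62.5% | 25/36 = 69.4% | 6.9 points |

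The documents give no value for k or S.

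**The case against.** The strongest reply is that the protocol already guards against unscanned progression. Section 4.5.5.1 states: "A full tumor assessment, including radiographic assessment, must be performed any time disease progression or relapse is suspected". Section 5.3.5.10 sits among the adverse-event recording rules, treats symptomatic progression as rare, and asks for objective documentation. This largely stands. A reader might infer that early clinical progressors in general are censored at Day 2; the documents do not support that. It takes a missing mandatory scan and no other event. The scan rule does not, however, help a patient who is scanned, shows no CT progression and is still taken off as progressive on PET-CT or symptoms.

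A reader might also infer that Section 2.2.3 counts any investigator-determined progression. It does not say so; it leaves the modality open within a PET-CT or CT framework.

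A third tempting inference is that a PET-only progression at end of induction in FL would be re-dated by about 6 months, to the 12-month CT. That CT belongs to the maintenance schedule. Maintenance is for patients with CR, PR or stable disease (Section 3.1.2.2), so a patient called progressive would not reach it. A CT is also scheduled at end of induction, and a new focus may already meet the CT criteria that day.

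Finally, CT-only may be a deliberate choice. Section 5.1.4.4 warns that lenalidomide tumor flare can look like progression, and Section 3.3.5.3 mentions false-positive PET-CT from immune-cell infiltration. This stands as a reason not to dictate the modality, but not as a reason to leave two definitions in force.

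**Conclusion.** The contradiction holds for all three endpoints and nothing in the current text resolves it. Under the CT-only version, censoring can be a consequence of failure: at the last tumor assessment for PFS, EFS and DFS, and at treatment start plus 1 for PFS and, more narrowly, EFS. The direction is upward, provided the investigator's call reflects true failure.

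The amount cannot be derived. The 2.5 to 3.6 points for 2 of 40 patients rest on an assumed count, an assumed 50% to 70% event-free share among the others and no other censoring. It would be wrong to read any particular number of such patients, or a concentration in DLBCL, into the documents.

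The consequence is limited. PFS, EFS and DFS are exploratory and summarized descriptively, with no test or decision rule. The primary endpoint, IRC-assessed PET-CT CR at end of induction, has its own rule for missing assessments and is untouched. The change should be made because it is cheap and these are the study's long-term efficacy measures.

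**What to change.** - Use one progression definition in the Synopsis, Section 2.2.3 and Section 6.6.3. The choice of modality is the sponsor's, with a sentence of reasons.
- State how PET-only progression and documented clinical progression without CT confirmation are counted and dated, and where such a patient is censored if not counted.
- Restrict plus-1 censoring to patients with no post-baseline information on disease status, and give the unit.
- Report the alternative definition (CT-only versus any investigator-determined progression) as a sensitivity curve, with the number of patients whose status differs.

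The cost is protocol and SAP wording and one extra exploratory analysis. Sample size and the primary analysis do not change.

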### **Pharmacokinetic Objective**

The pharmacokinetic (PK) objective for this study is to characterize the PK profiles of obinutuzumab, *rituximab*, polatuzumab vedotin, and lenalidomide when given in combination on the basis of the following endpoints:

- Observed serum obinutuzumab concentration at specified timepoints
- *Observed serum rituximab concentration at specified timepoints*
- Observed serum and plasma concentrations of polatuzumab vedotin and relevant analytes (total antibody, antibody-conjugated mono-methyl auristatin E, and unconjugated mono-methyl auristatin E) at specified timepoints
- Observed plasma lenalidomide concentration at specified timepoints

### **Immunogenicity Objectives**

The immunogenicity objective for this study is to evaluate the immune response to obinutuzumab, *rituximab*, and polatuzumab vedotin on the basis of the following endpoints:

- Incidence of human anti-human antibodies (HAHAs) to obinutuzumab during the study relative to the prevalence of HAHAs at baseline
- *Incidence of human anti-chimeric antibodies (HACAs) to rituximab during the study relative to the prevalence of HACAs at baseline*
- Incidence of anti-therapeutic antibodies (ATAs) to polatuzumab vedotin during the study relative to the prevalence of ATAs at baseline

The exploratory immunogenicity objective for this study is to evaluate potential relationships between HAHAs *or HACAs*, and ATAs on the basis of the following endpoint:

- Correlation between HAHA *or HACA*, and ATA status and *respective* efficacy, safety, or PK endpoints

### **Biomarker Objective**

The exploratory biomarker objective for this study is to identify non-inherited biomarkers that are predictive of response to study treatment (i.e., predictive biomarkers), are associated with progression to a more severe disease state (i.e., prognostic biomarkers), are associated with acquired resistance to study treatment, are associated with susceptibility to developing adverse events, can provide evidence of study treatment activity, can increase the knowledge and understanding of lymphoma biology or study treatment mechanism of action, or can contribute to improvement of diagnostic assays on the basis of the following endpoint:

- Association between non-inherited biomarkers and efficacy, safety, pharmacokinetics, or immunogenicity endpoints

